9.3.3.3.3 Unsolicited Adverse Events

In addition to recording solicited reactions, subjects' parent(s) / guardian(s) of subjects randomized into the Expanded safety analysis set will be instructed to record any other medical events that may occur during the 28-day period after each vaccination to be taken as per the study design. Space will be provided in the diary card for this purpose.

Information on SAEs will be collected and assessed throughout the study, from Day 0 until the 6-month follow-up phone call or end of influenza season surveillance. Any SAE occurring at any time during the study will be reported by the Investigator in the CRB according to the completion instructions provided by the Sponsor; this includes checking the “Serious” box on the AE CRF and completing the appropriate Safety Complementary Information CRFs. All information concerning the SAE is to be reported either as part of the initial reporting or during follow-up reporting if relevant information became available later (eg, outcome, medical history, results of investigations, copy of hospitalization reports). In case a subject experiences febrile convulsion (neurological event associating fever and seizure), the assessment will be performed according to the “Guideline for definition and collection of cases of febrile convulsion”, and this event will be considered an SAE. See [Section 10](#) for further details on SAE reporting.

For each unsolicited AE (whether serious or non-serious), the following information is to be recorded:

- Start and stop dates^a
- Intensity of the event:

For measurable unsolicited AEs that are part of the list of solicited reactions, the size of the AE as well as the temperature for fever will be collected and analyzed based on the corresponding scale used for solicited reactions (see [Table 9.2](#) and [Table 9.3](#)).

All other unsolicited AEs will be classified according to the following intensity scale:

^a The stop date of all related AEs will be actively solicited. For other events, the investigator will provide the stop date when it becomes available. AEs for which no stop date was obtained during the course of the study will be considered as ongoing at the end of the study.

- Grade 1
CRF: A type of adverse event that is usually transient and may require only minimal treatment or therapeutic intervention. The event does not generally interfere with usual activities of daily living
Diary card: No interference with usual activities.
- Grade 2
CRF: A type of adverse event that is usually alleviated with additional therapeutic intervention. The event interferes with usual activities of daily living, causing discomfort but poses no significant or permanent risk of harm to the research participant
Diary card: Some interference with usual activities.
- Grade 3
CRF: A type of adverse event that interrupts usual activities of daily living, or significantly affects clinical status, or may require intensive therapeutic intervention
Diary card: Significant; prevents usual activities.
- Whether the AE was related to the investigational product (for unsolicited systemic AEs)
The Investigator will assess the causal relationship between the AE and the investigational product as either “Not related” or “Related”, as described in [Section 9.3.3.3.5](#).
- Action taken for each AE (eg, medication)
The action(s) taken by the subjects' parent or guardian to treat and/or manage any unsolicited AEs will be classified in the CRB using the following list (all applicable items should be checked):
 - None
 - Medication
 - Health care provider contact
 - Hospitalized
 - Discontinuation of study vaccination
- Whether the AE was serious
For each SAE, the Investigator will complete all seriousness criteria that apply (outcome, elapsed time, and relationship to study procedures)
- Whether the AE caused study discontinuation

9.3.3.3.4 Adverse Events of Special Interest

AESIs will be captured as SAEs and will be collected throughout the study. These include new onset of GBS, encephalitis / myelitis (including transverse myelitis), Bell's palsy, convulsions, optic neuritis, and brachial neuritis [\(26\)](#) [\(27\)](#) [\(28\)](#).

9.3.3.3.5 Assessment of Causality

The Investigator will assess the ***causal relationship*** between each unsolicited systemic AE and the product administered as either ***not related*** or ***related***, based on the following definitions:

Not related – The AE is clearly / most probably caused by other etiologies such as an underlying condition, therapeutic intervention, or concomitant therapy; or the delay between vaccination and the onset of the AE is incompatible with a causal relationship; or the AE started before the first vaccination (screening phase, if applicable)

Related – There is a “reasonable possibility” that the AE was caused by the product administered, meaning that there is evidence or arguments to suggest a causal relationship

Note: By convention, all AEs reported at the injection site (whether solicited or unsolicited) and all solicited systemic AEs are considered to be related to the administered product and therefore are referred to as reactions and do not require the Investigator’s opinion on relatedness.

Adverse events likely to be related to the product, whether serious or not, that persist at the end of the study will be followed up by the Investigator until their complete disappearance or the stabilization of the subject’s condition. The Investigator will inform the Sponsor of the date of final disappearance of the event or the date of “chronicity” establishment.

9.4 Observational Endpoints and Assessment Methods

9.4.1 Efficacy

9.4.1.1 Efficacy Endpoints

- Occurrence of an ILI starting \geq 14 days after vaccination, laboratory-confirmed as positive for each circulating influenza A subtype and B lineage: A/H1N1, A/H3N2, B/Victoria and B/Yamagata
- Occurrence of an ILI starting \geq 14 days after first vaccination, laboratory-confirmed as positive in each age subgroup of subjects
- Occurrence of an ILI starting \geq 14 days after first vaccination, laboratory-confirmed as positive in each season
- Occurrence of an ILI starting \geq 14 days after first vaccination, laboratory-confirmed as positive in subjects previously unvaccinated
- Occurrence of an ILI starting \geq 14 days after first vaccination and before second injection, laboratory-confirmed as positive in subjects previously unvaccinated
- Occurrence of an ILI starting within 14-90 days after first vaccination, laboratory-confirmed as positive

- Occurrence of a modified CDC-defined ILI starting \geq 14 days after first vaccination, and laboratory-confirmed as positive
- For subjects enrolled in both Season 1 (NH) and Season 3 (NH), occurrence of an ILI starting \geq 14 days after first vaccination in Season 3 (NH), laboratory-confirmed as positive according to the vaccination pattern

Influenza-associated Events/ Health care utilization

The following events that are associated with ILI and occurring within 30 days after the ILI onset will be described for cases of laboratory-confirmed ILI caused by any viral type/subtype and for any ILI, respectively:

- Occurrence of AOM based on clinical diagnosis
- Occurrence of ALRI (eg, pneumonia, lower respiratory tract infection, bronchiolitis, bronchitis, and croup) based on clinical and/or x-ray diagnosis
- Occurrence, duration, and intensity of ILI symptoms
- Occurrence of medication use (eg, antibiotics, antivirals)
- Occurrence of hospitalizations
- Occurrence of emergency room visits
- Occurrence of non-routine medical office visits (including urgent care visits)
- Occurrence of absenteeism

9.4.1.2 Efficacy Assessment Methods

9.4.2 Immunogenicity

9.4.2.1 Immunogenicity Endpoints

Immunogenicity for correlate of protection

- HAI titer for each vaccine strain 28 days after the last vaccination, together with occurrence of an ILI starting \geq 14 days after vaccination, confirmed as positive for any influenza A or B type
- HAI titer for each vaccine strain 28 days after the last vaccination, together with occurrence of an ILI starting \geq 14 days after vaccination, laboratory-confirmed for viral strains similar to those contained in the vaccine

Antibody persistence

For subjects enrolled in both Season 1 (NH) and Season 3 (NH) and who are randomized to the Immunogenicity Subset, the HAI Ab titers against the 4 vaccine strains used in Season 1 (NH) will be measured at D0 before starting vaccination in Season 3 (NH). The following endpoints will be described.

- HAI individual titer on D0 and 28 days after the last vaccination of Season 1 (NH) and on D0 of Season 3 (NH)
- Detectable HAI titer, ie, with a titer ≥ 10 (1/dilution [dil]) at D0 and 28 days after the last vaccination of Season 1 (NH) and on D0 of Season 3 (NH)
- Subjects with titer ≥ 40 (1/dil) on D0 and 28 days after the last vaccination of Season 1 (NH) and on D0 of Season 3 (NH)

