- To describe in each vaccine group the use of antibiotics and antivirals that are associated with any ILI, within 30 days after the onset of the ILI
- To describe in each vaccine group hospitalizations that are associated with cases of laboratory-confirmed ILI, within 30 days after onset of the ILI
- To describe in each vaccine group hospitalizations that are associated with any ILI, within 30 days after onset of the ILI
- To describe in each vaccine group emergency room visits that are associated with cases of laboratory-confirmed ILI, within 30 days after onset of the ILI
- To describe in each vaccine group emergency room visits that are associated with any ILI, within 30 days after onset of the ILI
- To describe in each vaccine group non-routine medical office visits (including urgent care visits) that are associated with cases of laboratory-confirmed ILI, within 30 days after onset of the ILI

- To describe in each vaccine group non-routine medical office visits (including urgent care visits) that are associated with any ILI, within 30 days after onset of the ILI
- To describe in each vaccine group medication use that is associated with cases of laboratory-confirmed ILI, within 30 days after onset of the ILI
- To describe in each vaccine group medication use that is associated with any ILI, within 30 days after onset of the ILI
- To describe in each vaccine group absenteeism (Parent(s) / guardian's absenteeism due to child sick days) that is associated with cases of laboratory-confirmed ILI, within 30 days after onset of the ILI
- To describe in each vaccine group absenteeism (Parent(s) / guardian's absenteeism due to child sick days) that is associated with any ILI, within 30 days after onset of the ILI

Correlates of Protection Objective

To assess the association of HAI titers to the 4 vaccine strains with the occurrence of laboratory-confirmed ILI of any influenza A or B type, or of viral strains similar to those contained in the vaccine.

Antibody persistence

To describe the persistence of immune response 1 year after vaccination among subjects from Season 1 (NH) who are re-enrolled for Season 3 (NH) according to the vaccine received in Season 1 (NH).

The endpoints for the observational objectives are presented in [Section 9.4](#).

3 Investigators and Study Organization

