9.1 Definitions

Protocol-defined ILI: occurrence of fever $\geq 38^{\circ}\text{C}$ (100.4°F) concurrently with at least one of the following symptoms: cough, wheezing, difficulty breathing, nasal congestion, rhinorrhea, pharyngitis (sore throat), otitis, vomiting, diarrhea, shivering (chills), fatigue (tiredness), headache, or myalgia (muscle aches).

Modified CDC-defined ILI: occurrence of fever (defined as temperature $> 38^{\circ}\text{C}$ [$> 100.4^{\circ}\text{F}$]) with cough, pharyngitis, or sore throat

Laboratory-confirmed influenza: a positive influenza result on either polymerase chain reaction (PCR) or viral culture.

Culture-confirmed influenza: a positive influenza result on viral culture.

Genetic similarity: Genetic similarity is defined when a laboratory-confirmed isolate is deemed similar to one of the viral strains contained in the vaccine formulations according to sequencing of full HA gene segments proteins.

Antigenic similarity: Antigenic similarity is defined when a laboratory-confirmed isolate is deemed similar to one of the viral strains contained in the vaccine formulations according to Ferret Antigenicity testing (hemagglutination inhibition [HAI] against a panel of known standard ferret reference antisera).

Similarity to vaccine components: For prevention of laboratory-confirmed influenza illness caused by viral strains similar to those contained in the vaccine in subjects 6 months through 35 months of age, laboratory-confirmed isolate is deemed similar to one of the vaccine components based on antigenic similarity only. For all the other endpoints, similarity is based on antigenic similarity when available or based on genetic similarity otherwise.

ALRI: pneumonia, bronchiolitis, bronchitis, or laryngotracheobronchitis (croup) based on a clinical and/or x-ray diagnosis

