12.1.3 Statistical Methods for Observational Objective(s)

Estimation of efficacy for the observational objectives will be as described for the primary objective; for each estimate of efficacy, a 95% CI will be calculated.

Descriptive analysis and statistical models will be used to investigate [REDACTED] As this analysis is exploratory, several statistical approaches such as [REDACTED] [REDACTED]. These methods will be detailed in the SAP.

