- To describe in each vaccine group the use of antibiotics and antivirals that are associated with any ILI, within 30 days after the onset of the ILI
- To describe in each vaccine group hospitalizations that are associated with cases of laboratory-confirmed ILI, within 30 days after onset of the ILI
- To describe in each vaccine group hospitalizations that are associated with any ILI, within 30 days after onset of the ILI
- To describe in each vaccine group emergency room visits that are associated with cases of laboratory-confirmed ILI, within 30 days after onset of the ILI
- To describe in each vaccine group emergency room visits that are associated with any ILI, within 30 days after onset of the ILI
- To describe in each vaccine group non-routine medical office visits (including urgent care visits) that are associated with cases of laboratory-confirmed ILI, within 30 days after onset of the ILI

- To describe in each vaccine group non-routine medical office visits (including urgent care visits) that are associated with any ILI, within 30 days after onset of the ILI
- To describe in each vaccine group medication use that is associated with cases of laboratory-confirmed ILI, within 30 days after onset of the ILI
- To describe in each vaccine group medication use that is associated with any ILI, within 30 days after onset of the ILI
- To describe in each vaccine group absenteeism (Parent(s) / guardian's absenteeism due to child sick days) that is associated with cases of laboratory-confirmed ILI, within 30 days after onset of the ILI
- To describe in each vaccine group absenteeism (Parent(s) / guardian's absenteeism due to child sick days) that is associated with any ILI, within 30 days after onset of the ILI

Correlates of protection objective

To assess the association of HAI titers to the 4 vaccine strains with the occurrence of laboratory-confirmed ILI of any influenza A or B type, or of viral strains similar to those contained in the vaccine.

Antibody persistence

To describe the persistence of immune response 1 year after vaccination among subjects from Season 1 (NH) who are re-enrolled for Season 3 (NH) according to the vaccine received in Season 1 (NH).

3 Description of the Overall Study Design and Plan

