5.2.7 Immunogenicity Analysis Set

The IAS will be used for all descriptive immunogenicity objectives and is defined as the subjects in the main cohort randomized in the Immunogenicity Subset in Seasons 1, 2, and 3 and the subjects in the Re-vaccination Cohort in Season 3 who received at least one dose of the study vaccine and had one post-vaccination blood sample. Subjects will be analyzed as treated.

For analysis of immunogenicity by SN and ELLA methods, the subset of IAS with available results on the considered serological method will be used.

For correlate of protection assessment, subjects who are part of both the IAS and the FASE will be considered.

¹ other vaccines, blood products, immune-suppressors, immune-modulators with immunosuppressive properties, anti-proliferative drugs such as DNA synthesis inhibitors

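### The visible correlate-of-protection endpoints do not pair each strain's HAI titre with illness of the same subtype or lineage, which can distort the strain-specific associations

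*Protocol*

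**What the plan says.** Protocol 9.4.2.1 lists two correlate endpoints, repeated in the synopsis. Both start from "HAI titer for each vaccine strain 28 days after the last vaccination, together with occurrence of an ILI starting" 14 days or more after vaccination. In the first, the illness is "confirmed as positive for any influenza A or B type". In the second, it is "laboratory-confirmed for viral strains similar to those contained in the vaccine". Protocol 9.1 defines similarity by whether an isolate is "deemed similar to one of the viral strains contained in the vaccine formulations". That means any one of the components, not the one whose titre is being analysed.

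The objective has the same form in section 2.3 of both documents. The SAP begins it "To assess the association of HAI titers to the 4 vaccine strains with the occurrence of" and names the same two outcomes.

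The analysis is exploratory. Protocol 12.1.3 blacks out the approach and adds: "These methods will be detailed in the SAP". SAP 5.1.3.3, where it would stand, is also blacked out, heading included. What remains visible is the population, in SAP 5.2.7: "For correlate of protection assessment, subjects who are part of both the IAS and the FASE will be considered".

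Protocol 9.4.1.1 already has a case endpoint for each A subtype and B lineage, but only for relative efficacy. It is not paired with titres.

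**The concern.** HAI antibody is strain specific, and the protocol relies on this in 9.3.1.2, where ferret antisera are used to tell strains apart. Under the first endpoint, an H3N2 or B case counts against a child's H1N1 titre. Under the second, mismatched viruses are dropped, but an H3N2-like case still counts against the H1N1 titre.

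Two distortions can follow. Cases caused by other strains carry no information about a given titre's protection, so they can flatten its slope. And because a child who responds well to one strain may respond well to the others, a titre to a strain that never circulated can borrow an apparent effect.

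Protocol 1.4 bases the need for an efficacy trial on the lack of a proven quantitative correlate in children. A titre-risk relation from this trial is therefore likely to be used, and one that shifts with the season's strain mix would not carry over to other seasons.

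**Working it through.** The documents give no sample size, effect size or power for this objective that could be reproduced. The check is therefore a formula and a simulation, with every parameter assumed.

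**Formula.** Suppose titre s acts only on its own subtype, with log odds ratio b per unit, and subtype s makes up share p of all cases.

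- All four titres in one model, any-type illness: slope for titre s ≈ p × b.
- One titre at a time, common correlation rho between titres: slope ≈ [p + rho × (1 − p)] × b.
- Titre s against illness of subtype s: slope = b.

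**Illustration A.** Assumed: true ratio 0.70 per two-fold titre, titre SD 1.5 log2 units, attack rate about 6%, and shares of 50/30/20/0% for H1N1, H3N2, B/Victoria and B/Yamagata.

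- Four titres together: 0.70^0.5 = 0.84, 0.70^0.3 = 0.90, 0.70^0.2 = 0.93, 0.70^0 = 1.00.
- One at a time, rho = 0.6: the weights are 0.5 + 0.6 × 0.5 = 0.80, then 0.72, 0.68 and 0.60. So 0.70^0.80 = 0.75, 0.70^0.72 = 0.77, 0.70^0.68 = 0.78, 0.70^0.60 = 0.81.

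Simulated odds ratios, 400,000 subjects per scenario, in the order H1N1/H3N2/B-Victoria/B-Yamagata:

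| Correlation | Any type, one titre at a time | Any type, four titres together | Matched |
|---|---|---|---|
| 0 | 0.83/0.89/0.93/1.01 | 0.83/0.89/0.93/1.01 | 0.69/0.70/0.70/none |
| 0.3 | 0.78/0.83/0.85/0.89 | 0.83/0.89/0.93/1.00 | 0.70/0.69/0.69/none |
| 0.6 | 0.74/0.76/0.78/0.80 | 0.83/0.89/0.93/1.00 | 0.69/0.70/0.70/none |
| 0.8 | 0.71/0.72/0.73/0.74 | 0.83/0.89/0.93/1.01 | 0.69/0.69/0.69/none |

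The simulation agrees with the formula to within about 0.02. The matched analysis gives no estimate for a strain without cases, which is the right answer.

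**Other mixes, same assumptions.** With equal shares of 25%, the four-titre model gives 0.90 to 0.92 for every strain. With 90/10/0/0%, the dominant strain is hardly diluted (0.69 to 0.71). Each absent strain, modelled singly, reads 1.00 to 1.01 at rho = 0, 0.89 at 0.3, 0.80 at 0.6 and 0.73 at 0.8. Matched analysis gives 0.68 to 0.71 throughout.

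**Illustration B.** Assumed: true odds ratio 0.30 per log10, SD 0.5, attack rate 5%, shares 30/40/30/0%. With 60 cohorts of 20,000, single-titre any-type odds ratios are 0.68/0.61/0.70/1.00 at rho = 0, 0.53/0.48/0.52/0.69 at 0.3, and 0.40/0.38/0.40/0.47 at 0.6. A run with 1,000,000 subjects per scenario agrees within 0.02. Its four-titre model gives about 0.69/0.60/0.69, and 0.98 to 0.99 for the absent strain, at every correlation. Matched analysis recovers 0.28 to 0.30.

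**Reading.** Dilution is greatest when circulation is mixed and titres are weakly correlated. The spurious signal needs correlated titres and single-titre models. A four-titre model removes the spurious signal but not the dilution.

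**The case against.** The strongest reply is the redaction. Pairing by strain, and the choice between single-titre and joint models, belong to the analysis method, and that text is blacked out in protocol 12.1.3 and SAP 5.1.3.3. It was evidently substantive: SAP reference items 13 to 16 cover correlates of protection, proportion of effect explained, logistic regression and case-cohort variance. Blacked-out text is not missing text. This stands. A reader might infer that the plan fits one titre at a time, or that its analysis lacks strain matching; the documents show neither.

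Second, the endpoint lists data elements and does not prescribe four separate regressions. It fits a joint model, in which the spurious signal disappears. That also stands, but the dilution remains, so the endpoint wording still matters.

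Third, the sizes rest wholly on assumed inputs, and the simulated cohorts exceed the trial's 13,320 children, of whom only those in both the IAS and the FASE enter this analysis. The figures show direction and mechanism. They say nothing about precision in the real subset.

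Fourth, matching needs a subtype for each case. Protocol 9.3.1.2 gives PCR-positive, culture-negative samples no further testing, and the initial PCR in 9.2.1.2 separates only A from B. The any-type endpoint does not have this problem. It should therefore be kept beside the matched one.

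**Conclusion.** The point holds for the visible endpoints and objectives: neither pairs a strain's titre with illness of the same subtype or lineage. Under mixed circulation this can weaken the matching strain's slope whichever model is used. With correlated titres and single-titre models, it can also make an irrelevant titre look protective.

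Three stronger readings are tempting but unsupported. One is that the objective cannot yield a usable titre-risk relation; the redacted methods may already match by strain. Another is that dilution and spurious protection will both occur; the size and direction depend on strain mix, titre correlation and model, and high correlation weakens the first effect while strengthening the second. The third is that both endpoints use influenza of any type; only the first does, although the second still pools the four components.

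The effect is confined to an exploratory objective. No confirmatory test, alpha level or sample size depends on it. It is worth correcting because the change is cheap.

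**What to change.** In protocol 9.4.2.1, and in SAP 5.1.3.3 unless the redacted text already does so:

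- Make strain-matched pairs the main correlate analysis: HAI titre to strain s with laboratory-confirmed ILI of the same A subtype or B lineage and, second, with ILI similar to strain s.
- Keep the any-type and any-similar pairings as supportive, in a model with all four titres together.
- In the matched analysis, censor cases of other subtypes at onset or treat them as non-cases, and state which.
- Do not count confirmed cases of unknown subtype as non-cases. Exclude them or censor them at onset, and report their number.

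The synopsis and the objective text in section 2.3 of both documents should follow. The cost is wording: the subtype and lineage case endpoint in 9.4.1.1 already exists, so no new visits or samples are needed. The downside is fewer cases per strain, limited to those that can be subtyped.
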